Aim I. Assess mTOR inhibition safety in elderly human subjects, 70-95 years of age.

Prior human studies of mTOR inhibition by RAPA have focused on subjects with underlying health issues (transplant recipients, patients with cancer or autoimmunity, etc.) so RAPA was often used in combination with other immunosuppressive or anti-proliferative drugs. Thus, we propose to assess whether RAPA can be safely delivered to an otherwise healthy, but elderly test population. Towards this end, subjects will be placed on mTOR inhibition by RAPA (Rapamune, Wyeth/Pfizer) and an equal number on placebo. Their health status will be assessed by: i) physical examination, ii) clinical blood work iii) weekly self-reporting of complications to the clinical nurse, and iv) use of both a depression scale and the SF36 questionnaire. Participants will remain on drug therapy (either Rapa or placebo) for the entire ~2 months of the RAPA study.

Aim II. Assess the effects of mTOR inhibition on vaccine efficacy in the elderly.

Humoral immune responses decline with advancing age in humans as evidenced by decreased vaccine efficacy and increased susceptibility to infection. Thus, to determine whether mTOR inhibition by RAPA alters the age-associated loss in immune competence, study participants will be immunized with the seasonal flu vaccine (subjects will not have had prior exposure to the composition used). Both humoral (antibody titer) and cellular (T cell proliferation) responses will be assessed. In addition, the subjects will receive a second immunization to test effects on memory B (antibody) and T cell responses.

Aim III. Determine whether mTOR inhibition can improve general immune features in the aged

mTOR inhibition's effects on immune parameters characteristically altered by aging will be assessed. These include: i) serum cytokine levels (IL-6, TGF- β , etc.) as indicators of increased inflammation, ii) the naive to memory T cell ratio that decreases with age due to thymus involution and memory expansion; and iii) T cell functional subsets as assessed by fluorescence-activated cell sorting (FACS) for cell surface markers and cytokine measures.

Aim IV. Determine whether mTOR inhibition can improve muscle strength and cognitive function

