Step-by-Step Methods:**Methods for Sub-study A & B Rapamycin**

mTOR inhibition: Subjects will be randomized to mTOR inhibition by RAPA or placebo in equal sized groups. Those receiving the drug will be started on 1 mg per day with no loading dose. Dosage will be adjusted for a target whole blood concentration of 10-15 ng/ml and maintained there until the study's conclusion. RAPA blood levels will be determined by mass spec. The initial trough level will be drawn one week after initiation of therapy. When a maintenance dose is adjusted, the new dose will be maintained for 7 days before additional adjustments are made based on concentration monitoring. Reported adverse reactions to RAPA and related agents when used as solitary agents include mucositis, pneumonitis, skin rash, hyperlipidemia, hyperglycemia, thrombocytopenia, and anemia.

Clinical assessment: Subject health will be confirmed initially by history and physical exam, normal laboratory tests (fasting lipid profile, metabolic profile, CBC, and CK), and 12-lead EKG. Oral glucose tolerance test (OGTT): Baseline (fasting) samples for determination of glucose, insulin, and free fatty acid (FFA) concentrations will be drawn at -30, -15 and -0 min (these basal values are averaged). At time zero, each subject will ingest 75 g of glucose. Glucose, insulin and FFA are determined every 30 min for 2 h following glucose ingestion. The Matsuda index of insulin sensitivity will be calculated from OGTT results, as described (Matsuda and DeFronzo, 1999). At each visit, patients will receive a standard history, physical examination, blood chemistry assessment, and be queried in detail for RAPA adverse reactions including infections. A questionnaire (SF-36) designed to assess the benefits of health care interventions and the Geriatric Depression Scale questionnaire will allow us to characterize any adverse or beneficial effects. Between visits, subjects will be contacted weekly by the Clinical Nurse to ensure that no complications have arisen. Blood test for CK will be monitored.

If subjects have previously undergone all or part of screening labs/tests within the past 4 months, the data may be accepted for eligibility determination without screening labs or procedures having to be repeated.

Aim II. Assess the effects of mTOR inhibition on vaccine efficacy in the elderly.

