Approach The advent of next generation DNA sequencing has revolutionized efforts to characterize the endogenous microbiome. In fact, these genomic-based technologies have revealed many new bacterial species that were missed using microbiologic and serologic approaches. The endogenous microbiota plays a critically important role in generating an efficacious immune system and a healthy functioning gut. Of relevance to this proposal, the microbiome also regulates susceptibility to obesity and diabetes. An oral medication, like ACA, will likely target the gut microbiome. Thus, subjects will self-collect feces in sterile containers and deliver it to the clinic at their regular visits. DNA isolation will be performed by the Genomics Core facility on a fee-for-service basis and the samples will be delivered to the Sequencing Core Facility for analysis. The bacterial rDNA in each fecal sample will be amplified using primers from conserved regions of the 16S ribosomal RNA genes. Amplified DNAs are then used to generate a library which is subsequently subjected to deep (next gen) sequencing.

Expected Results For humans, there have been many reports documenting the bacterial species that dominate in older vs. young individuals (24). Given the ages of our subjects, we would expect to see a profile more similar to the “old” profile. It would be most exciting if ACA were to alter the microbiome, making it more “youthful”.

Sub-study D Rapamycin Alone – Cardiovascular Effects

For Aims D-1, D-2, D-3, and D-4:

Intervention with RAPA will begin at the end of Visit 2 once all screening and baseline measurements have been collected. Subjects will self-administer RAPA once daily for a period of 8 weeks (56 doses) and there will be no placebo group in this Sub-study. We will screen 12 MALE subjects to complete 6. No females will be enrolled in this pilot substudy.

Clinical assessment: See also Sub-study A (except without OGTT). In substudies A, B and C, no detrimental diabetogenic effects of RAPA were found, i.e. OGTT, FBS, HbA1c were unaltered by RAPA.

If subjects have previously undergone all or part of screening labs/tests within the past 4 months, the data may be accepted for eligibility determination without screening labs or procedures having to be repeated.

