GDS (Geriatr Depression Scale)*			X	X		X	X	X	X		X
CLOX Assessment (cognitive assessment)*		X		X							
PET/MRI								0	0		0

Notes: X=scheduled procedure; O=optional procedure (if funding found and subject consents) *May be done over Visit 0 and Visit 1; #=procedure performed if > 2 weeks from prior measure at V1

Table 2. VISIT SCHEDULE: Sub-study D. Rapamycin Alone – Cardiovascular Effects

VISIT NUMBER	V1	V2	FU1	V3	FU2	V4
Visit goal	Consent/ screen (fasting)	Pre-drug (not fasting)	Phone follow up*	4 wks RAPA	Phone follow up*	8 wks RAPA
Week number		0	1	4		8
PROCEDURES	2-2.5h	3-3.5		2.5-3		4
Consent form and CLOX>10	✓					
SAFETY/AEs/METABOLIC						
Physical exam	✓	✓		✓		✓
ECG	✓					✓
Self reported Adverse Events (AEs)	✓	✓	✓	✓	✓	✓
CBC (blood cell counts)	✓			✓		✓
Fasting blood sugar/CMP	✓			✓		✓
Fasting lipids	✓					✓
HbA1c	✓					✓
Urinalysis	✓					✓
IMMUNE FUNCTION						
Serum for cytokine profiles	✓			✓		✓
Flow cytometry: T cell subsets	✓			✓		✓
T cell activation potential	✓			✓		✓
RAPAMYCIN LEVEL						✓
Meal/snack	✓					✓
COGNITIVE FUNCTION						
Geriatric depression scale		✓				✓
EXIT, SLUMS, TAPS		✓				✓
VR-36 QOL		✓				✓
PHYSICAL FUNCTION						
Hand grip and 40 foot walk		✓		✓		✓
Garmin VivoFit3 Activity Monitor	DISPENSE	BRING*		BRING*		BRING*
DISPENSE STUDY MED		✓		✓		
VASCULAR FUNCTION						
Aortic Pulse Wave Velocity (PWV)	✓**	✓**		✓		✓
Arteriolar Endothelial Function (LDF)	✓**	✓**		✓		✓
CARDIAC/CEREBRAL BLOOD FLOW FUNCTION						
MRI		✓				✓
Schedule MRI - Date						

*Telephone follow up of subjects to assess tolerability and or adverse reactions to RAPA will be conducted at least once between V2 and V3. If tolerating well after 1-2 weeks of RAPA treatment without side effects, no further calls may be necessary. If side effects are reported at any time during RAPA administration, the investigator may choose to modify dosing, if appropriate, and follow by phone on a weekly basis until resolved.

BRING* – At Visits 2, 3 and 4, subjects will bring their Garmin VivoFit3 Activity Monitor so that activity data can be downloaded to a protected server with adequate storage and backup.

**Depending on availability of subjects, shared lab equipment and personnel resources, the vascular function assessments for baseline measurements may be scheduled and performed at Visit 1 OR Visit 2. This allows flexibility and promotes protocol compliance.

Item 7

Risks Section. Risks are described in detail in the Step 2-Institutional Form.

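### Sub-study D has three inconsistent rules for adverse-event contact between visits, and the loosest makes the intensity of questioning depend on what a man has already reported

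*Combined protocol and SAP*

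**What the plan says.** Three places in the protocol bear on how often men in Sub-study D are asked about AEs between clinic visits.

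- **Item 6, Sub-study D, clinical assessment.** The text is a cross-reference: "Clinical assessment: See also Sub-study A (except without OGTT". No other exception is named. The clinical-assessment paragraph for Sub-studies A and B says: "Between visits, subjects will be contacted weekly by the Clinical Nurse to ensure that no complications have arisen". Aim I in Item 4, which covers A and B, likewise lists "weekly self-reporting of complications to the clinical nurse".
- **Table 2, visit schedule for Sub-study D.** The row beginning "Self reported Adverse Events (AEs" is ticked in all six columns: V1, V2, FU1, V3, FU2 and V4. FU1 is placed at week 1. FU2 lies between V3 (week 4) and V4 (week 8), but its week is blank. Both FU columns are headed "Phone follow up" with an asterisk.
- **Footnote to that asterisk.** A call "will be conducted at least once between V2 and V3". Then: "If tolerating well after 1-2 weeks of RAPA treatment without side effects, no further calls may be necessary". Where a man does report a side effect, early or late, the investigator may "follow by phone on a weekly basis until resolved". The footnote sets no minimum for the interval between V3 and V4.

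**The concern.** Study staff could follow this protocol in good faith and make six calls to a man or one. If they follow the footnote, the number of times he is asked depends on what he has already said. A man who reports side effects may be called every week; a man who reports none in the first week or two need not be called again.

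This matters because the abstract (Item 2) gives measuring indicators of health, to ensure safe delivery of RAPA in the elderly, as part of what Sub-study D does. The sub-study has no placebo group and plans for 6 completers, so a few unrecorded events would change its AE summary noticeably. Longer recall intervals make it more likely that mild or short-lived events are forgotten.

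**Working it through.** The documents state no figure on this point, so the check is a count of contacts and gaps under each rule.

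**Inputs.** RAPA is taken for 8 weeks, 56 doses (Item 6, Sub-study D). V2 is week 0, V3 week 4, V4 week 8 and FU1 week 1 (Table 2). The week of FU2 is not given, so weeks 5, 6 and 7 are each tried as assumptions. For the footnote minimum, the single call is assumed to fall at week 1 or week 2. Only the on-treatment period is counted.

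**Formulas.** Between-visit calls = contacts other than those at weeks 0, 4 and 8. On-drug AE contacts = calls + 2 (V3 and V4). Longest gap = largest difference between successive contact weeks.

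| Rule | Contact weeks | Calls | On-drug AE contacts | Longest gap |
|---|---|---|---|---|
| Weekly, through the reference to Sub-study A | 0, 1, 2, 3, 4, 5, 6, 7, 8 | 6 | 6 + 2 = 8 | 1 week |
| Table 2 as ticked | 0, 1, 4, FU2 (5, 6 or 7), 8 | 2 | 2 + 2 = 4 | 4 − 1 = 3 weeks (FU1 to V3), wherever FU2 falls |
| Footnote minimum | 0, 1 or 2, 4, 8 | 1 | 1 + 2 = 3 | 8 − 4 = 4 weeks (V3 to V4) |

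Under the footnote minimum, the gap from the single call to V3 is 4 − 2 = 2 to 4 − 1 = 3 weeks. The V3 to V4 gap covers 4 of the 8 weeks, or 28 of the 56 doses. The FU2 tick is the only item Table 2 schedules in that interval.

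**Dependence on earlier reports.** If a man reports side effects at week 1 that do not resolve, and the investigator follows him weekly, he has calls at weeks 1, 2, 3, 5, 6 and 7, which is 6. A man who reports none may have 1.

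**Calls added, measured from the footnote minimum.**
- FU2 for everyone: (2 − 1) × 6 completers = 6 calls.
- Weekly for everyone: (6 − 1) × 6 = 30 calls.
- Up to 12 men are screened. If all 12 were dosed, which is a ceiling, the figures would be 12 and 60.

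**The case against.** The other side has good arguments, and several of them limit the point.

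**The weekly rule may not bind Sub-study D.** The cross-reference is loosely worded, and the data analysis plan says Sub-study D procedures will typically follow Table 2. Table 2 also departs from Sub-study A in more than the glucose test: it lists the VR-36 where Sub-study A uses the SF-36, and it has no CK row. A telephone rule specific to D could reasonably be taken to govern. This stands as far as it goes: inheritance of the weekly rule is arguable. But nothing exempts D from it either. Against Table 2 alone, the footnote costs one call and one extra week of gap.

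**The footnote does not contradict FU2.** A reader might infer that it does. Both FU column heads carry the asterisk, so the footnote qualifies them. What remains is ambiguity: FU2 has a tick and no week, and the footnote never says whether it is required.

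**AE collection is not absent in symptom-free men.** A reader might infer that as well. Every man gets at least one call before V3 and is asked about AEs, with a physical examination and blood tests, at V3 and V4. The footnote also covers side effects reported at any time on RAPA. Only the intensity of questioning and the recall interval differ.

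**A safety comparison with Sub-studies A and B is not planned.** It would be tempting to say D will look safer than A and B. No passage plans that comparison, Aims D-1 to D-4 are not safety aims, and no event rates are given. It can be said only that D's AE record would be collected differently from theirs. Nor do the documents give onset times for RAPA reactions, so no claim about late-onset events rests on them.

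Item 7 refers to a separate institutional form for risks. That form is not part of these documents and may address monitoring.

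**Conclusion.** The inconsistency is real and modest. Sub-study D can be run with 6, 2 or as few as 1 between-visit AE calls, and with longest gaps of 1, 3 or 4 weeks, depending on which text is followed. The 6-call figure assumes that the reference to Sub-study A carries the weekly rule across. The 1-call figure assumes that the footnote governs and that its permission to stop is used. The 3-week gap holds for FU2 at week 5, 6 or 7.

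The consequence is report-dependent intensity of AE ascertainment, with longer recall and possible under-reporting of mild or transient events. With no placebo group, this is not a bias between arms within D; it affects the AE frequencies described in about 6 completers. The size of any under-reporting cannot be estimated, because the documents give no event rates. The change is worth making because it is cheap and removes a real ambiguity. Which contact frequency is clinically right is not judged here.

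**What to change.** Reconcile the clinical-assessment paragraph for Sub-studies A and B, the cross-reference in Sub-study D, and Table 2 with its footnote, so that they state one AE data-collection schedule for Sub-study D. The sponsor chooses the frequency. The schedule should:

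- apply to every man, whatever he reported earlier;
- say whether FU2 is required and in which week it falls;
- remove or amend the clause that allows calls to stop, so that it matches;
- leave extra calls for men with side effects as additional, with AEs found on them recorded separately from those found at scheduled contacts.

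The footnote's wording on dose modification is outside this point.

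The cost is a few short phone calls. From the footnote minimum, this is about 6 in total for 6 completers if FU2 applies to all and about 30 under the weekly rule, with somewhat more if men who do not complete are also dosed.
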